#### 7.1.2 Derivation of endpoints from eDiary data

The eDiary data are filled in by the subject on a daily basis during a 3-week baseline period (starting at V2) and every 4 months after randomisation for a period of 14 days 3 weeks prior to V5 (at 4 months), V6 (at 8 months), V7 (at 12 months), V8 (at 16 months), V9 (at 20 months), V10 (at 24 months) and V11 (25-30 months).

Only days where diary data has been entered are considered for calculating scores. For baseline data, only data collected before the date of first dose will be considered.

When calculating the baseline scores, if a subject has at least 14 days of diary data, the first 7 days are disregarded, and the following 14 days of data are used to calculate the scores. This means that a subject with 22 days of data will have baseline scores based on the data collected from day 8 to day 21 both days included. If instead the subject had 20 days of diary data, the baseline scores would be based on the 13 days of data collected from day 8 to day 20, both included.

When calculating baseline scores, if a subject has less than 14 days of diary data, the last 7 of these are used for calculating baseline scores, if the subject has less than 7 days of diary data, all data will be used.

For non-baseline periods the last 14 days of diary data are used.

The 14 days of diary records prior to visit 5, 6, 7, 8, 9, 10, and 11 will define the 14 days eDiary assessment period used for calculating the endpoints.

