The use of leukotriene receptor antagonists (LTRA) is permitted as concomitant medication for continued use on same dose only but will not be provided.

Flow chart

Table 1 Flow chart¹⁵

Visit ID:	V1	TC1	V2	TC2	V3	V4	TC3, 4	V5	TC5, 6, 7	V6	TC8, 9, 10	V7	TC11, 12, 13	V8	TC14, 15, 16	V9	TC17, 18, 19	V10 ¹⁶	TC20	V11 ¹⁸	TC21	UN
Visit:	Screen ing	Reten- tion	Base- line	Mid base- line call	Ran- domi- sation	Visit 4		Visit 5		Visit 6		Visit 7		Visit 8		Visit 9		Visit 10		Final visit	Follow -up	Un- sche- duled visit
Time ¹⁹ from randomisation (IMP initiation) for all visits and TCs, except for visit 11 (actual date of visit)	Max 12 wk before V3		- 3 wk - 7 d	- 2 wk ± 2 d	-	+ 4 wk + 7 d	+ 2m ±2d + 3m ±2d	+ 4m ± 7 d	+ 5m ±2d + 6m ±2d + 7m ±2d	+ 8m ± 7 d	+9m ±2d +10m ±2d +11m ±2d	+ 12m ± 7 d	+13m ±2d +14m ±2d +15m ±2d	+ 16m ±7 d	+17m ±2d +18m ±2d +19m ±2d	+ 20m ± 7 d	+21m ±2d +22m ±2d +23m ±2d	+ 24m ± 7 d	2 wk prior to V11 ± 2 d	30 Apr ± 7 d	+ 2 wk from V11 + 7 d	
Informed consent and assent ²⁰	х																					
Demography	Х																					
Medical history incl. evaluate previous asthma exacerbations	x																					
SPT ²¹	х		(X)																			
Review of in-/exclusion criteria	х		x		x																	

¹⁵ To the extent possible, all examinations scheduled for the final visit must be performed on subjects who receive the IMP but do not complete the trial according to the protocol. If poss ble, the TC follow-up (TC21) should be performed and the corresponding eCRF pages should be filled in.

¹⁶ Visit 10 is not applicable for subjects randomised in cohort 1 after 31-Mar-2018; for subjects randomised in cohort 2 after 31-Mar-2019, for subjects randomised in cohort 3 after 31-Mar-2020 and for subjects randomised in cohort 4 after 31-Mar-2022, if applicable.

¹⁷ TC20 performed 2 weeks prior to final visit.

¹⁸ Visit 11 will take place on 30-Apr-2020 \pm 7 days for cohort 1, 30-Apr-2021 \pm 7 days for cohort 2, 30-Apr-2022 \pm 7 days for cohort 3 and 30-Apr-2024 \pm 7 days for cohort 4.

¹⁹ One month (m) is considered 30 days.

²⁰ Obtain written informed consent for the trial, storage of serum samples in the ALK Research Biobank, and for pharmacogenetics testing, before any other trial procedures are performed.

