4.2 Exclusion criteria

- E1. Has a clinically relevant history and is sensitised, symptomatic, and regularly exposed to animal dander, molds, and/or cockroach (e.g., present in the home, job, school, etc.) or other perennial allergen
- E2. Has experienced a life-threatening asthma attack defined for this protocol as an asthma episode that required intubation and/or was associated with hypercapnia requiring non-invasive ventilator support
- E3. Within the last month before the randomisation visit (visit 3), has had an occurrence of any clinical deterioration of asthma that resulted in emergency treatment, hospitalisation, or treatment with systemic corticosteroids
- E4. Within the last 3 months before the randomisation visit (visit 3) while on high dose ICS treatment, has had an occurrence of any clinical deterioration of asthma that resulted in emergency treatment, hospitalisation, or treatment with systemic corticosteroids
- E5. SLIT treatment with *D. pteronyssinus* or *D. farinae* for more than 1 month within the last 5 years. In addition, any SLIT treatment with *D. pteronyssinus* or *D. farinae* within the previous 12 months
- E6. SCIT treatment with *D. pteronyssinus* or *D. farinae* reaching the maintenance dose within the last 5 years. In addition, any SCIT treatment with *D. pteronyssinus* or *D. farinae* within the previous 12 months
- E7. Ongoing treatment with any allergy immunotherapy product
- E8. Severe chronic oral inflammation
- E9. Any nasal or naso/oropharyngeal condition that could confound the efficacy or safety assessments (e.g., hypertrophy of the pharyngeal/palatine tonsils, clinically relevant nasal polyps, a history of paranasal sinus surgery or surgery of nasal turbinates)⁵²
- E10. Any clinically relevant chronic disease incl. malignancy that in the opinion of the investigator would interfere with the trial evaluations or the safety of the subject
- E11. Has a diagnosis or history of eosinophilic oesophagitis
- E12. A relevant history of systemic allergic reaction e.g. anaphylaxis with cardiorespiratory symptoms, generalised urticaria or severe facial angioedema that in the opinion of the investigator may constitute an increased safety concern
- E13. Active or poorly controlled autoimmune diseases, immune defects, immunodeficiencies, immunosuppression or malignant neoplastic diseases with current disease relevance

⁵² If in doubt, nasal endoscopy is recommended

- E14. Ongoing treatment with OCS

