9.2 Precautions in relation to first dosing

First intake of IMP should be at the clinic with a minimum of 30 minutes observation period after the intake. For the recording of onset and duration of solicited AEs that occur on Day 1 (visit 3), the subject should remain in the clinic for 60 minutes after IMP intake.

Prior to IMP intake an oropharyngeal examination should be performed. This should be repeated 60 minutes after IMP intake.

For subjects with severe oral inflammation (e.g. oral lichen planus, mouth ulcers or thrush), oral wounds or following oral surgery, including dental extraction, or following tooth loss, initiation of IMP treatment should be postponed until the oral cavity has healed.

For subjects with symptoms of, or in treatment for, upper respiratory tract infection, acute sinusitis, acute otitis media or other relevant infections, initiation of IMP treatment should be postponed until the condition has improved.

For subjects with a severe asthma exacerbation within the last 30 days prior to randomisation treatment initiation should be postponed by minimum 30 days from the time of the severe asthma exacerbation (start of OCS treatment or first day of hospitalisation). The treatment initiation can be postponed maximum 3 times.

Only subjects meeting all inclusion criteria listed in Section 4.1 and none of the exclusion criteria in Section 4.2 are considered eligible for randomisation and first dosing.

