### Figure 1 Overview of trial design

Period 1 is the screening period.

Period 2 is the 3-week baseline period during which eligible subjects will fill in their asthma and rhinoconjunctivitis symptoms and medication use in an electronic diary (eDiary). Only the 2 last weeks of the 3-week baseline period will be used for calculation of baseline scores. At the start of period 2 (visit 2) subjects' regular asthma rescue mediation and rhinoconjunctivitis rescue medication will be replaced with the rescue medication provided by ALK.

Period 3 is the treatment initiation and maintenance period to allow the treatment with the HDM SLIT-tablet to take effect. It starts at randomisation and lasts for 4-10 months. Period 3 ends the 31st of August. During the first 28 days of period 3, 15 prespecified symptoms occurring after IMP intake will be assessed by the subject/parent/caregiver in the eDiary. The reported symptoms will be evaluated by investigator and reported, based on the investigator's medical evaluation and discretion, in the eCRF as solicited AEs.

Period 4 is the efficacy assessment period for the primary endpoint. Period 4 begins on September 1st for all subjects and lasts until the end of trial or discontinuation from IMP. During this period, the rate of clinically relevant asthma exacerbations will be evaluated.

Every 4 months after randomisation, subjects or their parent/caregiver will be asked to complete the eDlary for a period of 14 days 3 weeks prior to V5 (at 4 months), V6 (at 8 months), V7 (at 12 months), V8 (at 16 months), V9 (at 20 months), V10 (at 24 months) and V11 (25-29 months).

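### Treatment duration runs from randomisation, so a postponed first tablet lowers computed compliance and can drop a child just above 80% from the per-protocol set; a smaller point concerns long baseline diaries

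*SAP*

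**What the plan says.** **Compliance.** SAP 4.5.1.2 measures treatment duration from the randomisation date to the last IMP intake, both included, and notes that interruptions may fall inside it. SAP 4.5.1.4 divides tablets taken by that duration. SAP section 3 removes children below 80% from the per-protocol set, which SAP 4.2.5 uses for a supportive analysis of the primary endpoint. Protocol 15.6 also divides doses used by the length of the treatment period, but does not say when that period starts.

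First intake is planned for visit 3, the randomisation visit. Protocol Table 6 lists randomisation ahead of the oropharyngeal examination and the first tablet. Section 9.2 and footnotes 56 and 57 defer the first tablet until an oral lesion has healed or an infection has improved. The definition of treatment-emergent events in SAP 4.5.2 starts at first IMP administration.

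**Baseline diary.** For at least 14 recorded pre-dose days, SAP 7.1.2 states that "the first 7 days are disregarded, and the following 14 days of data are used to calculate the scores". Its example is that "a subject with 22 days of data will have baseline scores based on the data collected from day 8 to day 21". For later periods: "For non-baseline periods the last 14 days of diary data are used". The design section of the SAP (1.2) says: "Only the 2 last weeks of the 3-week baseline period will be used for calculation of baseline scores".

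**The concern.** A compliance figure should compare tablets taken with tablets due. A child randomised at visit 3 and then held back for a mouth ulcer, a lost tooth or a respiratory infection has no tablet due until the hold ends. The SAP denominator still counts those days. The error goes one way: computed compliance can only be too low, so a child can be wrongly removed from the per-protocol set but never wrongly kept. A delay that the protocol requires would be treated as poor adherence.

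The companion point has the same character. Counting the diary window from its start means that, in a record longer than 21 days, the days closest to first dose are left out. The later periods, and baseline records shorter than 14 days, are counted from the end. The diary baseline is the covariate in the models for nocturnal awakenings and SABA days, and in the symptom-score models. The possible loss is some covariate precision.

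**Working it through.** **Compliance**

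Let T be the days from randomisation to last intake (inclusive), g the days from randomisation to first intake, and n the tablets taken.

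- Compliance since first intake: c = n / (T - g).
- Compliance under the SAP: n / T = c x (T - g) / T.
- The SAP figure is below 80% whenever c is below 80 x T / (T - g).

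For T, the protocol lets treatment start between 1 November and 10 April, and period 4 ends on 30 April. Taking cohort 2, with last intake on that date:

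- Start 10 Apr 2019, end 30 Apr 2021: 731 + 20 + 1 = 752 days.
- Start 1 Nov 2018, end 30 Apr 2021: 731 + 180 + 1 = 912 days.

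The gap g is not in the documents. I assume 7, 14 and 28 days. With g = 0 the factor is 1 and nothing changes.

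| T (days) | g (days) | (T - g)/T | True compliance needed to reach 80% |
|---|---|---|---|
| 752 | 7 | 745/752 = 0.991 | 80 x 752/745 = 80.8% |
| 752 | 14 | 738/752 = 0.981 | 80 x 752/738 = 81.5% |
| 752 | 28 | 724/752 = 0.963 | 80 x 752/724 = 83.1% |
| 912 | 7 | 905/912 = 0.992 | 80 x 912/905 = 80.6% |
| 912 | 14 | 898/912 = 0.985 | 80 x 912/898 = 81.2% |
| 912 | 28 | 884/912 = 0.969 | 80 x 912/884 = 82.5% |

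Example: with T = 752, g = 14 and 600 tablets taken, compliance since first intake is 600/738 = 81.3%. The SAP figure is 600/752 = 79.8%, and the child leaves the per-protocol set.

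The effect is larger for short exposure. The per-protocol set also requires 6 months in period 4, so a near-minimal case is 10 Apr 2019 to 1 Mar 2020, T = 327. The limits are then 80 x 327/320 = 81.8%, 80 x 327/313 = 83.6% and 80 x 327/299 = 87.5%.

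**Baseline diary**

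The rule for m recorded pre-dose days (m at least 14) is days 8 to the smaller of m and 21. It reproduces both SAP examples: m = 22 gives days 8-21, and m = 20 gives days 8-20 (13 days). The last 14 days would be days m - 13 to m.

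| m | SAP window | Last 14 days | Latest days omitted by the SAP | Days shared |
|---|---|---|---|---|
| 21 | 8-21 | 8-21 | 0 | 14 |
| 22 | 8-21 | 9-22 | 1 | 13 |
| 25 | 8-21 | 12-25 | 4 | 10 |
| 28 | 8-21 | 15-28 | 7 | 7 |

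Records of 22 to 28 days are possible without any postponement, because the flow chart places visit 2 between 21 and 28 days before randomisation.

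**The case against.** **On compliance.** Randomisation and first intake are planned for one visit, and the protocol flow chart treats them as the same time point: "from randomisation (IMP initiation) for all visits and TCs, except for visit 11 (actual date of visit". The order of procedures in Table 6 is stated as a preference, and a careful site would examine the mouth before randomising. No document shows that a gap occurred. The SAP knowingly leaves untreated days in the denominator, since it allows interruptions. Only a supportive analysis and a summary table depend on it, and the Appendix 4 list is not in the published copy, so nobody near 80% can be identified.

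Most of this stands as a limit on size. The interruption clause does not answer the point: it covers pauses once treatment has begun, not days before a first tablet.

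A reader might go further and infer gaps of 30 to 90 days from section 9.2, where "treatment initiation should be postponed by minimum 30 days from the time of the severe asthma exacerbation" and "The treatment initiation can be postponed maximum 3 times". The documents do not support that. Exclusion E3 bars a child who "Within the last month before the randomisation visit (visit 3), has had an occurrence of any clinical deterioration of asthma" leading to emergency treatment, hospitalisation or systemic corticosteroids. Footnote 55 sits at a step before randomisation. After a severe exacerbation the whole of visit 3 should move, leaving no gap between randomisation and intake. Only footnotes 56 and 57 leave room for one.

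**On the diary.** The 22-day case is settled in advance by a worked example, and every rule agrees for the planned 21 days. Later diaries last 14 days and have no first week to discard, so the comparison with them is imperfect. A reader might also infer that a postponed child records a second full diary and gets a baseline from the first, exacerbation included. No sentence describes a repeated or continued diary, so at most that is a missing detail.

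**Conclusion.** The compliance point holds as a small, correctable flaw. For any child whose first tablet comes after the randomisation date, the SAP rule understates compliance. With an assumed gap of 7 to 28 days in completers, computed compliance is multiplied by 0.963 to 0.992, and children with true compliance from 80% up to 80.6-83.1% fall below the cut-off. How many children had a gap, and how many sit in that band, is unknown. The consequence stops at the compliance summary and the supportive per-protocol analysis.

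The diary point is minor: a choice of window that could be better aligned for records longer than 21 days, not a contradiction in the plan.

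A reader might infer that either rule favours one arm. Nothing supports that. Both rules apply alike to the two arms, and the postponements and diary days concerned precede the first dose in a double-blind trial. The primary analysis on the full analysis set and the FEV1 analysis use neither quantity.

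**What to change.** **SAP 4.5.1.2:** define treatment duration as the date of first IMP intake to the date of last IMP intake, both included. Then re-check the 80% criterion once, blinded, against the per-protocol list in Appendix 4. The first-intake date is already needed to define treatment-emergent events, and every child in the full and safety sets has taken at least one dose. Nothing changes for children dosed on the day of randomisation. The change needs no protocol amendment, visit or patient burden. SAP version 4.0 states that it was approved before database lock and unblinding, so the re-check belongs before that step.

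**SAP 7.1.2 (optional):** if more than 21 recorded days exist before first dose, use the last 14 recorded days before first dose; otherwise keep the present rule. This matches the rule for later periods. The cost is a shift of 1 to 7 days in the window for children with 22 to 28 recorded days, and the SAP's 22-day example becomes days 9-22.

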#### Average rhinitis, and rhinoconjunctivitis DSS

Rhinoconjunctivitis symptoms are recorded on a daily basis during the periods of eDiary recording. The rhinoconjunctivitis symptoms consist of 4 rhinitis symptoms (runny nose, blocked nose, sneezing, itchy nose) and 2 conjunctivitis symptoms (gritty feeling/red/itchy eyes and watery eyes) which are scored from 0 to 3 as shown in Table 6.

Type of document Document ID	Date: Version: Status:	11-Aug-2022 4.0 Final	
INTERNAL USE	Page:	49 of 79	

#### Table 6 Subjects' symptom scoring

Scored by	Definition of score	Numerical
subject		Score
No symptoms	No sign/symptom evident	0
Mild symptoms	Symptom clearly present, but minimal awareness; easily tolerated	1
Moderate symptoms	Definite awareness of symptom that is bothersome but tolerable	2
Severe symptoms	Symptom that is hard to tolerate; causes interference with activities of daily living and/or sleeping	3

 Scoring scales are not seen by the subjects

The rhinitis DSS is the total of the 4 individual rhinitis symptom scores and ranges from 0 to 12.

#### .

The rhinoconjunctivitis DSS is the total of all 6 individual rhinoconjunctivitis symptom scores and ranges from 0 to 18.

Table 7 shows the construction of the DSS.

Table 7	Construction	of DSS
---------	--------------	--------

Symptoms	Rhinitis DSS	Rhinoconjunctivitis DSS
Rhinitis symptoms		
Runny nose	0-3	0-3
Blocked nose	0-3	0-3
Sneezing	0-3	0-3
Itchy nose	0-3	0-3
Conjunctivitis symptoms		
Gritty feeling/red/itchy eyes		0-3
Watery eyes		0-3
Total range	0-12	0-18

The average symptom scores (average rhinoconjunctivitis DSS, average rhinitis DSS, average rhinitis DSS, are for each subject and each visit (V2, V5, V6, V7, V8, V9, V10, V11) calculated as the average of non-missing records during the 14 days of eDiary assessment.

Type of document	Date:	11-Aug-2022	
Document ID	Version:	4.0	
	Status:	Final	
INTERNAL USE	Page:	50 of 79	

# 7.1.2.1 Average rhinitis, and rhinoconjunctivitis daily medication score (DMS)

Use of rhinoconjunctivitis symptomatic medication is recorded daily during the periods of eDiary recording.

The total daily medication score for each symptomatic medication is calculated as the unit score multiplied by the number of units entered in the daily diary, see **Table 8**.

The rhinitis DMS: the sum of the total daily scores for all rhinitis symptomatic medication ranges from 0 to 12.

The rhinoconjunctivitis DMS: the sum of the total daily scores for all rhinitis/conjunctivitis symptomatic medication ranges from 0 to 20.

The average daily medication scores (average rhinoconjuntivitis DMS, average rhinitis DMS,

are for each subject and each visit (V2, V5, V6, V7, V8, V9, V10, V11) calculated as the average of non-missing records during the 14 days of eDiary record period.

Type of document Document ID	Date: Version:	11-Aug-2022 4.0	
	Status:	Final	
INTERNAL USE	Page:	51 of 79	

#### Table 8 Daily medication score

Rescue medication	Subject dosing instruction 	Score/ Dose unit 	Maximum daily score
Rhinitis medication score			
Desloratadine tablets  , 5 mg	< 6 years old: 2.5 ml once daily	4	4
Or	6-11 years old: 5 ml once daily		
Desloratadine Oral solution 0.5 mg/ml	At least 12 years: 1 tablet once daily		
Mometasone furoate nasal spray, 50 µg/dose	<12 years old: 1 puff in each nostril once daily	4/PUFF	8
	At least 12 years: 2 puffs in each nostril once daily	2/PUFF	
Maximum daily rhinitis DMS⁴			12
Conjunctivitis DMS⁴			
Desloratadine tablets  , 5 mg	5 years old: 2.5 ml once daily	2	2
Or	6-11 years old: 5 ml once daily	1	
Desloratadine Oral solution 0.5 mg/ml	At least 12 years: 1 tablet once daily		
Azelastine eye drops, 0.5 mg/ml	1 drop in each eye twice daily	1.5/drop	6
Maximum daily rhinoconjunctivitis DMS⁴			20

 When calculating scores that depend on the age of the subject, the age attained at the start of the diary period is used. This age is calculated from the partial birthdate.

Scoring scales are not seen by the subjects.

Desloratadine will count 4 in the rhinitis score and 2 in the conjunctivitis score, based on assumed equal efficacy of antihistamine on the 4 nasal symptoms and 2 eye symptoms (Salmun and Lorber 2002).

When calculating the desloratadine score, the amount of desloratadine used in mg is calculated regardless of it being syrup or tablets, and that amount is used to calculate a fraction of the associated score for the subject.

 If any subject exceeds the recommended daily dose of symptomatic medication, the maximal daily score will be used.

Type of document	Date:	11-Aug-2022	
Document ID	Version:	4.0	
	Status:	Final	
INTERNAL USE	Page:	52 of 79	

#### 7.1.2.2 Average TCRS and rhinoconjunctivitis TCS

TCRS: the sum of the rhinitis DSS and the rhinitis DMS and ranges from 0-24.

The rhinoconjunctivitis TCS: the sum of the rhinoconjunctivitis DSS and the rhinoconjunctivitis DMS and ranges from 0-38.

The average total combined scores (average rhinoconjunctivitis TCS, average TCRS, average conjunctivitis TCS) are for each subject and each visit (V2, V5, V6, V7, V8, V9, V10, V11) calculated as the average of non-missing records during the 14 days of eDiary.

7.1.2.3 The average rhinitis and rhinoconjunctivitis CSMS recommended by EAACI task force

The rhinitis and the rhinoconjunctivitis CSMS are based on the daily rhinoconjunctivitis symptoms and medication use reported in the eDiary.

The rhinitis DSS and the rhinoconjunctivitis DSS according to the EAACI task force (**Pfaar et al. 2014**) are the sum of each individual DSS divided by the number of symptoms.

The rhinoconjunctivitis DMS according to EAACI task force (Pfaar et al. 2014) is a stepwise scoring method as shown in Table 9.

# Table 9 Stepwise scoring of rhinitis/conjunctivitis medication use according to the EAACI task force

Step	Rhinitis/Conjunctivitis Medication	Score
1	oral and/or topical (eyes or nose) nonsedative H1 antihistamines	1
2	intranasal corticosteroids	2
3	oral corticosteroids	3

The CSMS according to the EAACI task force is applied to the data in the current trial even though rhinitis/conjunctivitis rescue mediation is not taken in a stepwise manner and even though oral corticosteroids are not supplied as rhinitis/rhinoconjunctivitis rescue medication and are thus not assessed in the eDiary in MT-11. The CSMS scoring applied in the current trial is shown in Table 10.

The average rhinoconjunctivitis CSMS and average rhinitis CSMS is for each subject and each visit (V2, V5, V6, V7, V8, V9, V10, V11) calculated as the average of non-missing records during the 14 days of eDiary assessment.

Type of document Document ID	Date: Version: Status:	11-Aug-2022 4.0 Final	ALK
INTERNAL USE	Page:	53 of 79	

